13.2 Anticipated Adverse Device Effects

The following potential risks and complications are known to be associated with cerebral angiography, intracranial catheterization, intracranial stent/ flow diverters placement and would not be considered as UADEs:

- Allergic reaction, including but not limited to, imaging contrast dye, nitinol metal, and any other medications used during the procedure;
- Aneurysm rupture;
- Aneurysm growth;
- Bleeding including intracerebral, retroperitoneal or in other locations (Note: reportable events involving bleeding are not limited to those related to the procedure);
- Blindness;
- Cardiac arrhythmias;
- Cranial neuropathy;
- Device fracture, migration or misplacement;
- Device thrombosis;
- Diplopia;
- Dissection or perforation of the parent artery;
- Emboli;
- Failure to deliver the device;
- Failure to deploy the device at the intended target site;
- Headache;
- Hemorrhage;
- Hematoma / Hypoperfusion;
- Infection;
- Injury to normal vessel or tissue;
- Ischemia;
- Mass effect;
- Myocardial Infarction;
- Neurological deficits;
- Occlusion of non-target side branches;
- Pseudoaneurysm formation;
- Renal failure;
- Stenosis of stented segment;
- Seizure;
- Stenosis or thrombosis of the parent artery or a side branch vessel;
- Stroke or TIA (Transient Ischemic Attack);
- Thromboembolic event;

- Total occlusion of treated parent vessel segment;
- Vasospasm;
- Vessel perforation;
- Visual impairment.

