Additionally, other safety endpoints will also be assessed based on Adverse Events. The number of subjects and the number of adverse events per subjects will be presented for Adverse Events, unanticipated Adverse Events, Serious Adverse Events, and unanticipated Serious Adverse Events. The results will be provided by system organ class and preferred term. Narrative case summaries will be provided for each Serious Adverse Event. Two-sided 95% credible intervals will be presented for each adverse event with ≥5% incidence.

Technical Failures

Technical failure subjects will be presented separately but will be excluded from the ITT and Per Protocol populations if they did not receive the device. They will be included in the Safety population.

A FRED procedure will be categorized as a technical failure if the following occurs:

- Failed FRED Device Deployment Due to Technical Issues with the FRED Device
 - If the FRED Device enters the blood stream and cannot be deployed secondary to technical issues with the device itself (e.g., FRED Device malfunction or failure to access the target site due to the FRED Device), the Subject will be counted as enrolled with intent-to-treat. This will be considered as a secondary endpoint failure. The Subject will be maintained within the study and will not be replaced by another Subject. The Subject will be monitored for any Adverse Event for one (1) week

following the failed deployment due to a technical issue related to the FRED Device. Unless medically necessary to pursue treatment sooner, it is recommended that further attempts to treat the target aneurysm be deferred for a minimum of one (1) week so that any potential procedural Adverse Events may be monitored.

- Failed Device Deployment Due to Issues Related to the Procedure

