- A written report shall be submitted to the Investigation Site IRB/EC and Sponsor of any Unanticipated Adverse Device Effect as soon as possible (i.e. within 24 hours) but no later than 10 working days after the investigator first learns of the effect;
- A written report shall be submitted to the Sponsor regarding a withdrawal of study approval from the IRB/EC within 5 working days;
- A progress report shall be submitted to the Sponsor, Monitor and IRB/EC at regular intervals but no less than on a yearly basis. The report to the IRB/EC shall include a request for approval to continue the study. The status of the study shall be shared with the IRB/EC and Sponsor upon request.

- If a FRED System is used without obtaining informed consent, a report shall be provided to the IRB/EC and Sponsor within 5 working days after the use occurs.
- The Sponsor shall be notified of any deviation from the Clinical Investigation Plan/Protocol to protect the life or physical well-being of a Subject in an emergency. The notice shall be provided as soon as possible (i.e. 24 hours) but no later than 5 working days after the emergency occurred. If it is not an emergency, prior approval from the Sponsor shall be required for changes in or deviations from the protocol.
- Any proposed amendments to the protocol or informed consent form that have IRB/EC approval shall be submitted in written form to the Sponsor.
- The IRB /EC shall be notified of any changes to the status of the study including completion, termination or other necessary changes, according to the IRB policies in place at that institution.
- A letter of notification of the completion, termination or discontinuation of the study shall be submitted to the IRB/EC.
- A final report shall be submitted to the IRB/EC and Sponsor within 3 months after termination or completion of the study.

The Principal Investigator shall maintain accurate and complete records relating to the study. These records shall include:

- The Clinical Investigation Plan/Protocol and any documentation (date and reason) for each deviation from the protocol
- All correspondence including required reports
- Records of receipt, use and disposition of the investigational device
- Records of each Subject's case history and exposure to the investigational device

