13.0 Adverse Events

13.1 Definitions

- **Adverse Event (AE):**

Any unfavorable and unintended sign (including laboratory findings), symptom or disease that occurs to a subject while enrolled in this clinical investigation. Medical conditions that exist at study enrollment are not considered an AE unless condition worsens after use of the study device or antithrombotic medications.

- **Serious Adverse Event (SAE):**

A serious adverse event is any medical experience regardless of its relationship to the study treatment that occurs during subject enrollment in this trial that results in any of the following: (1) inpatient hospitalization or prolongation of a hospitalization; (b) persistent or significant disability/incapacity; (c) death of the study subject, or (d) necessitates an intervention to prevent a permanent impairment of a body function or permanent damage to a body structure.

- **Unanticipated Adverse Device Effect (UADE):**

Any serious adverse effect on health or safety or any life-threatening problem or death caused by or associated with a device, if that effect, problem or death was not previously identified in nature, severity or degree of incidence in the investigational plan or IDE application (including a supplementary plan or application), or any other unanticipated serious problem associated with a device that related to the rights, safety or welfare of subjects.

The common terminology criteria for adverse events (CTCAE) will be utilized for Adverse Event (AE) reporting. The CTCAE v.4.0 incorporates certain elements of the MedDRA terminology and the list is incorporated into the Manual of Operating Procedures.

Table 2 Adverse Event Reporting and Device Malfunction

Classification	Reporting time	Type of report
Unanticipated Adverse Device Effects (UADE)	Within 24 hours of learning of event; no more than 10 working days from learning of event	Adverse Event Reporting Form to be submitted to the sponsor, CRO and IRB according to the IRB policies in place at that institution. ¹
Serious AE (SAE)	Within 24 hours of learning of event; no more than 10 working days from learning of event	Serious Adverse Event Reporting Form to be submitted to the sponsor, CRO and IRB according to the IRB policies in place at that institution. ¹
Non-serious AE	Within 30 working days of event.	Adverse Event Reporting Form in EDC

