Device Malfunctioning With or Without Adverse Event	Within 5 working days of learning the event	Investigational Clinical Device Product Complaint and Return Form to be submitted to the sponsor, CRO and IRB according to the IRB policies in place at that institution. In case of death, it should be submitted to the FDA, Sponsor, CRO and IRB according to the IRB policies in place at that institution. ¹

¹ Note: Participating clinical sites have different IRBs that sometimes have varying Adverse Event reporting policies. Some request that all AEs be reported; others only request that only the SAEs and UADEs be reported. Regardless of this direction by site specific IRBs, MicroVention and its associated CROs require sites to report all AEs (including UADE reporting, serious AE, Non serious AE, Device Malfunction with or without AE) in an appropriate timeframe. No limitation of the reporting of adverse events are made by the sponsor (MicroVention), CRO and FDA.

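### Protocol 13.2 excludes 35 listed complications from UADE status by type alone, in conflict with the severity and incidence tests in the 13.1 definition

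*Protocol*

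**What the plan says.** **Definition (Protocol 13.1).** A serious adverse effect, life-threatening problem or death caused by or associated with the device is a UADE if it "was not previously identified in nature, severity or degree of incidence in the investigational plan or IDE application". The definition adds a residual limb: "or any other unanticipated serious problem associated with a device that related to the rights, safety or welfare of subjects".

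**Exclusion (Protocol 13.2).** The section is headed as anticipated device effects. It presents its list as complications already known from cerebral angiography, "intracranial catheterization, intracranial stent/ flow diverters placement and would not be considered as UADEs". There are 35 bullets, each naming a type of event, for example "Stroke or TIA (Transient Ischemic Attack"). None gives an expected severity or frequency, and the lead-in does not refer to 13.1.

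**Where the label is used.**
- Protocol 8.0: "A written report shall be submitted to the Investigation Site IRB/EC and Sponsor of any Unanticipated Adverse Device Effect", with no condition about local IRB policy.
- Protocol 6.2, under adverse events: subject and event counts "will be presented for Adverse Events, unanticipated Adverse Events, Serious Adverse Events, and unanticipated Serious Adverse Events".
- Protocol Table 2: UADEs and SAEs have the same deadline, "Within 24 hours of learning of event; no more than 10 working days from learning of event".
- Note to Table 2: whatever the local IRB asks for, "MicroVention and its associated CROs require sites to report all AEs".

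**The concern.** The definition offers three routes to being unanticipated: nature, severity and degree of incidence. The 13.2 list settles the matter on the first alone. Several bullets are broad (hemorrhage, ischemia, neurological deficits, injury to normal vessel or tissue), and one bullet holds both a transient ischemic attack and a stroke of any severity. Many serious neurovascular device effects would fit at least one of them.

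A known type of complication that proves worse or more common than expected is the case that the severity and incidence tests exist to catch. If investigators work from the list, that case will not carry the UADE label. Sites could also classify the same event differently, depending on which section they consult. At stake are consistent classification, the written report to the IRB/EC, and the content of the summaries of unanticipated events.

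**Working it through.** No arithmetic applies. Neither section contains a figure, and the point does not depend on alpha, power, sample size or an event rate. The check sets the two sections side by side and then traces the use of the label.

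**1. The two rules, for a serious device-associated event**

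| Event | 13.1 | 13.2 |
|---|---|---|
| Type not on the list | UADE if not previously identified | Silent; 13.1 decides |
| Type on the list, severity and frequency as identified | Not a UADE | Not a UADE |
| Type on the list, severity beyond that identified | UADE | Not a UADE |
| Type on the list, incidence beyond that identified | UADE | Not a UADE |

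The rules agree in the first two rows and conflict in the last two.

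**2. Does either section yield to the other?** No. 13.2 does not say that it is subject to 13.1, and it does not claim to override it. The protocol states no order of precedence, so the result for a listed event is ambiguous and is not settled in favour of exclusion.

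**3. Is death excluded?** Death is not a listed item, and 13.1 names death separately from effects and problems. A death following a listed complication can therefore still be a UADE under 13.1.

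**4. What happens to an event that a site leaves unlabelled?**
- Sponsor: it arrives as an SAE within the same time limits (Table 2, and note 3 to the Summary of Events).
- Clinical events committee: it adjudicates all adverse events (SAP 2 and 4.1).
- DSMB: it reviews mortality and major morbidity about every three months and applies stopping rules, whose content is not given (Protocol 13.6).
- IRB/EC: the unconditional written report in 8.0 is not triggered. The Table 2 route for SAEs remains.
- Summaries: Protocol 6.2 counts unanticipated AEs and SAEs separately. Because 13.2 is headed as anticipated effects, its list would probably be used to sort events there too, although the protocol does not say so.

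The conflict therefore affects classification, the 8.0 report and, probably, the 6.2 summaries. It does not affect capture of the event.

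**The case against.** The strongest reply is that this is a drafting inconsistency with little practical effect. Much of that stands.

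- A reader might infer that an unexpectedly severe or frequent device effect could never be classified as unanticipated. The text does not support this. Only listed types are touched, the 13.1 definition and its residual limb stand unamended, and 13.2 claims no precedence.
- A reader might infer from Table 2 that IRBs would not hear of these events. Table 2 uses the same deadline and the same deference to local IRB policy for UADEs and SAEs, so it draws no contrast between them. Its note describes two kinds of IRB policy, and both receive SAEs. The distinction rests on section 8.0 alone.
- A reader might infer that the sponsor would lose a review of changing risk. No visible section ties such a review to the UADE label.
- A reader might infer that the trial would report no unanticipated events by construction. Unlisted events remain eligible, and 13.2 speaks of UADEs whereas 6.2 speaks of unanticipated AEs and SAEs. SAP 8 plans no unanticipated-event table, so this part of the point concerns Protocol 6.2 only.

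Expected severities or rates may be stated in the IDE application or the Manual of Operating Procedures, neither of which is available here. That would supply the benchmark 13.1 needs, but it would not cure 13.2, whose exclusion refers to no benchmark.

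The reply does not remove the conflict itself. Two sections of one protocol give opposite answers for the same event, and a mandatory report depends on which is followed.

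**Conclusion.** The point holds as a conflict between two stated rules. For 35 listed complications, 13.2 decides UADE status by type, whereas 13.1 also requires severity and degree of incidence to be considered. A site following 13.2 would misclassify a serious, device-associated listed event whose severity or frequency exceeded what had been identified.

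The consequences are limited to the written IRB/EC report in 8.0 and, on the assumption that the 13.2 list is used to sort events for 6.2, the summaries of unanticipated events. Sponsor reporting, adjudication, DSMB review and the primary endpoints are unaffected. The number of events involved cannot be estimated, because the documents supplied give no expected rates for the listed items. The change is worth making because a safety definition should not be contradicted by the list meant to support it, and the correction is small.

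**What to change.** Reconcile the two sections by rewriting the 13.2 lead-in, for example: *The following effects are anticipated in nature. A listed event is still a UADE if it meets the definition in 13.1 because its severity or degree of incidence exceeds that identified in the investigational plan or IDE application.*

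Apply the same rule when events are classified for the unanticipated AE and SAE summaries in Protocol 6.2, and state there that it is the rule used.

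The cost is one sentence in 13.2, one in 6.2, and a classification step on events that the clinical events committee already adjudicates. The downside is that a few more events will be reported as UADEs. No endpoint, hypothesis, sample size or visit changes.

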13.3 Reporting of Adverse Events by Subjects

All subjects shall be instructed to report any adverse events to the Principal Investigator or Study Coordinator at hospital discharge and during the following 12 months.

Details and criteria regarding the procedure and the site's responsibility for reporting adverse events are described in the Manual of Operating Procedures.

13.4 Device Malfunction

If a device does not meet the specific performance requirements, per the provided Instructions for Use, the issue/incident must be reported. Reporting directions are described in the Manual of Operating Procedures. Another device shall be available to the physician to complete the procedure.

If the device malfunction results in an adverse event, it must be reported according to the directions in the Manual of Operating Procedures.

13.5 Post-Procedure Management of Adverse Events

Subjects will be evaluated at the scheduled follow-up visits. If any adverse events occur outside the follow-up schedule, additional follow-up should occur. The procedure for this is described in the Manual of Operating Procedures.

13.6 Data & Safety Monitoring Board (DSMB)

The purpose of the DSMB is to evaluate the relative treatment effects based on protocol-specified endpoints to determine if the trial is meeting its objectives. The DSMB will periodically assess the clinical trial data including but not limited to enrollment, device performance, mortality and major morbidity clinical outcomes, and make recommendations to MicroVention accordingly. The DSMB, which is referred to herein as The Board will provide these recommendations to ensure consistency with the objectives of the trial and appropriate ethical requirements.

The Board shall be formed prior to commencing the study. The Board shall have direct communication with the Primary Investigator of the study.

Each member of The Board shall have no financial or proprietary interest in the investigational device or the study itself. The Board will meet with the Primary Investigator prior to study initiation to review this Protocol and the Manual of Operating Procedures.

The Board will meet and review trial data at

- the earlier of three (3) months or after approximately 20 subjects (+/- 5) have been enrolled in the study and their data is available
- approximately every three (3) months thereafter depending on and commensurate with the rate of enrollment, and
- as needed if specific concerns arise.

The DSMB will provide recommendations to the Sponsor consistent with the objectives of the study and appropriate ethical requirements.

The primary objectives of the DSMB will include:

- Protect subject welfare
- Preserve study integrity by providing an independent review of data relating to safety and efficacy
- Review study data and make recommendations to stop, suspend, continue or modify the study based on serious concerns about subjects' safety, inadequate performance or rate of enrollment or observed beneficial or adverse effects of the treatment under the study
- Review risk/benefit profile of the device based on ongoing clinical study results
- Evaluate the progress of the trial, including periodic assessments of the data quality, participant risk versus benefit and other factors that can impact study outcomes
- Provide corrective actions for study centers that do not comply with study protocol or that perform unsatisfactorily
- Make recommendations, when appropriate, to increase the number of study centers or extend the enrollment period and/or study duration
- Ensure the outcomes of the meetings are based upon unbiased and comprehensive evaluation of the data
- Communicate findings, other recommendations or concerns as appropriate.

The DSMB may be asked to review final study results and recommend to the Sponsor modifications for future studies.

To minimize bias of its members, The Board shall be blinded to subject identities, Principal Investigators and investigational sites, to the extent possible.

Members of The Board shall include leading experts in neurology, interventional neuroradiology, and/or endovascular neurosurgery. None of the members of The Board shall be Principal Investigators in this study. The membership of The Board is contained in the appendix of the DSMB Charter.

Stopping Rules have been written and The Board will evaluate safety based on these rules. Any Board recommendations for study modification or termination because of concerns over patient safety, or issues relating to the data monitoring or quality control, shall be submitted immediately in writing and by verbal communication to the Primary Investigator for consideration and final decision.

14.0 Data Management

14.1 Data Quality Assurance

The sponsor (or designee) shall be responsible for training the appropriate personnel at each investigational site.

The sponsor (or designee) shall review the method of identifying and enrolling the appropriate subjects into the study.

The sponsor (or designee) shall provide the necessary documents and forms to assist each investigational site on subject recruitment, procedural follow-up, and the completion of forms for the study.

Each site shall be responsible for assuring uniform data collection and protocol compliance as required by the Clinical Investigation Plan/Protocol and associated documents.

14.2 Data Accuracy and Verifiability

All CRFs and other study documentation shall be filled out completely and clearly, copies of which shall be submitted to the sponsor upon request. CRFs and other study documents that are incomplete, or for which data is unclear, shall be replaced or completed upon request of the sponsor and then resubmitted to the sponsor upon request. A detailed description of the CRF completion and submission process is provided in the Manual of Operating Procedures.

It is the responsibility of the Principal Investigator from each investigational site to ensure that all data pertinent to the study be collected and entered into the study's secure data sharing website. The website will be maintained by an independent data management company and the sponsor shall have "view only" access. All data entered must be backed up by source documents. Copies of these documents will be stored in the site's study files and made available as requested by the sponsor for monitoring purposes.

15.0 Monitoring

The Sponsor shall select a Monitor(s) qualified by training and experience to monitor the study. A Monitor may be an employee of the Sponsor or an organization contracted by the Sponsor. The Monitor shall assure that the investigators are complying with the signed investigator agreement, the Clinical Investigation Plan/Protocol, IDE regulations and any conditions of approval imposed by the Investigation Site IRB/EC or FDA. Routine monitoring will occur to:

- verify that subject enrollment is being achieved;
- verify that the inclusion/exclusion criteria has been met at enrollment;
- verify that the correct version of the informed consent has been signed by the subject;
- review the medical records of all enrolled subjects to ensure all adverse events have been captured and properly reported;
- verify that the data and imaging are accurate, complete and backed up by source documents;
- verify that all contracts, certifications, and medical licenses for each site are valid through the duration of the study.

